9.2 POPULATIONS FOR ANALYSES

Analysis Population	Definition
Safety Population	All enrolled subjects who receive any amount of study drug comprise the Safety Population for safety and exposure analyses.
Imaging Population	All enrolled subjects who received any amount of study drug and who have at least one set of acceptable color fundus photographs and OCT scans predose and at least 3 acceptable quality fundus autofluorescence images during each of the following imaging sessions: predose, postdose: 5 minutes to 1 hour.
Pharmacokinetic (PK) Population	All enrolled subjects who receive any amount of study drug and who have at least one post-baseline PK sample will comprise the PK Population.

Abbreviations: OCT, optical coherence tomography.

9.3 STATISTICAL ANALYSES

9.3.1 General Approach

A formal statistical analysis plan (SAP) and data management plan will be developed and finalized before study database lock. The following is a summary of statistical approach:

- Variables used for sample size calculation will be calculated and presented for pooled populations and each subject population.
- All disposition, demographic, baseline characteristic and concomitant medication summaries will be presented by arm.
- Continuous variables: Descriptive statistics will include the number of non-missing values (n), arithmetic mean, standard deviation (SD), median, minimum and maximum

values. 90% Confidence Intervals (CIs), least-square (LS Means) values and Ratio for Geometrics LS means will also be displayed when appropriate.

- Categorical variables: Descriptive statistics will include counts and percentages per category. The denominator in all percentage calculations will be the number of subjects in the relevant analysis population with non-missing data, unless specifically stated otherwise. Percentages will be displayed to one decimal place. Proportions will be displayed to 3 decimal places.

9.3.2 Safety Analyses

Continuous safety data will be summarized with descriptive statistics (arithmetic mean, standard deviation [SD], median, minimum, and maximum) overall, by treatment, and by nominal visit/time point (where applicable).

Categorical safety data will be summarized with frequency counts and percentages overall and within dose level. Adverse events will be coded by system organ class and preferred term using the most current Medical Dictionary for Regulatory Activities (MedDRA) version available. The number of subjects experiencing treatment-emergent adverse events as well as maximum severity and relationship to study drug will be summarized.

Laboratory evaluations, vital signs assessments, and ECG parameters will be summarized at protocol-specified collection time point. A summary of change-from-baseline at each protocol-specified time point will also be presented.

Concomitant medications will be listed by subject and coded using the most current World Health Organization drug dictionary.

Medical history will be listed by subject and coded using MedDRA.

Further details will be provided in the SAP.

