All retinal images will be deidentified and sent in batches to a reading center for masked assessment. Assessors will be masked to type of subjects, their disease, dose, clinical status of subjects, and sequence of post-injection images. This provides an objective assessment of the ability of AMDX-2011P to identify amyloidogenic deposits. During the interim analysis, the SMC may also review representative images to confirm the optimum detection and the residence time and make potential recommendations to the retinal imaging time point(s) and/or potential safety assessment modifications.

Study Population:	Adult subjects with neurodegenerative diseases: Up to 36 adult male and female subjects diagnosed with Parkinson's disease, MSA or ALS.
Description of Sites/Facilities	The study will be conducted at 4-5 Phase 1 ophthalmology experienced sites located in the United States.
Enrolling Subjects:	
Description of Study drug:	AMDX-2011P is a novel retinal tracer indicated for the diagnosis of amyloid angiopathy. It is a phosphate prodrug hydrolyzed in vivo to the pharmacologically active molecule AMDX-2011.
Study Duration:	Estimated time to complete study from enrollment to completion of data analyses will be 7 months.
Subject Duration:	For each subject, study participation is expected to last up to 8 days: one day of dosing, 7 days of follow-up, and a window of up to 42 days to complete the screening procedures.

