7 STUDY DRUG DISCONTINUATION AND SUBJECT DISCONTINUATION/WITHDRAWAL

7.1 STOPPING RULES

The SMC will monitor safety throughout the study. The SMC will meet periodically to review available safety data to make decisions regarding continuation, modification, suspension, or termination of the study.

Study Stopping Rules

Dose escalation or administration of study drug in a dose cohort may be stopped and additional subjects will not receive study drug until a consultation has taken place among the investigator, the Study Medical Monitor (or designee), and SMC if one of the following circumstances occurs in subjects treated with AMDX-2011P unless it is determined by the SMC in consultation with investigator and the Study Medical Monitor that the occurrence is not related to the administration of the study drug:

- Two or more subjects in a cohort experience a Common Terminology Criteria for Adverse Events (CTCAE) Grade 3 or higher clinical or laboratory abnormality that is considered to be related to study drug by the investigator.
- An AE or group of AEs that singularly or in aggregate suggests to the investigator or Sponsor that the study drug is poorly tolerated and further treatment per protocol may not be safe.
- If one or more subject(s) in a cohort experience any treatment-related, treatment-emergent SAEs, dose escalation will be stopped to re-evaluate the dose in question.

If any of these criteria occur, the SMC will review all available data; if an event is determined to be related to a specific dose level, doses in subsequent cohorts may be modified or dose escalation may be terminated. Prior to any required dose level adjustment, the clinical and laboratory safety parameters from the previous dosing cohort(s) will be reviewed and discussed by the SMC to allow a recommendation on advancing to the next dose level. The suggested next doses may be the protocol-defined escalation dose, an equivalent dose, an intermediate dose, or an adjusted-downward dose based on evaluation of safety and tolerability data from previous cohorts.

The Sponsor, investigator, and the IRBs reserve the right to terminate or suspend the study at any time; the reason for such decision must be recorded. Should this occur, all data available will also be recorded in eCRFs. The investigator should notify the IRB in writing of the study's completion or early termination.

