8.2.4 **Clinical Safety Laboratory Assessments**

- See Section 10.2 for the list of clinical laboratory tests to be performed and the SoA (Section 1.3) for the timing and frequency.
- The investigator must review the laboratory report, document this review, and record any clinically relevant changes occurring during the study in the AE section of the eCRF. The laboratory reports must be filed with the source documents. Clinically

significant abnormal laboratory findings are those that are not associated with the underlying disease, unless judged by the investigator to be more severe than expected for the subject's condition.

- All laboratory tests with values considered clinically significantly abnormal during participation in the study should be repeated until the values return to normal or baseline or are no longer considered clinically significant by the investigator or Study Medical Monitor.
 - If such values do not return to normal/baseline within a period of time judged reasonable by the investigator, the etiology should be identified, and the Medical Monitor notified.
 - All protocol-required laboratory assessments, as defined in Section 10.2, must be conducted in accordance with the laboratory manual and the SoA (Section 1.3).
 - If laboratory values from non-protocol-specified laboratory assessments performed at the institution's local laboratory require a change in subject management or are considered clinically significant by the investigator (e.g., SAE or AE), then the results must be recorded in the eCRF.

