10.2 CLINICAL LABORATORY TESTS

- The tests detailed in [Table 8](#) will be performed by the local laboratory.
- Protocol-specific requirements for inclusion or exclusion of subjects are detailed in Section [5](#) of the protocol.
- Additional tests may be performed at any time during the study as determined necessary by the investigator or required by local regulations.
- Investigators must document their review of each laboratory safety report in subject's source records.

Table 8 Protocol-Required Safety Laboratory Assessments

Laboratory	Parameters
Serum Chemistry	Aspartate aminotransferase (AST), alanine aminotransferase (ALT), total and conjugated bilirubin, alkaline phosphatase (ALP), gamma-glutamyl-transferase (g-GT), creatine phosphokinase (CPK), albumin, creatinine, urea, total protein, sodium, chloride, calcium, phosphate, potassium, triglycerides, total cholesterol, glucose (fasting)
Hematology	Hemoglobin, hematocrit, erythrocytes (RBC), reticulocytes, platelets, leukocytes (WBC), differential (counts): neutrophils, basophils, eosinophils, lymphocytes, and monocytes
Coagulation	International normalized ratio (INR), activated partial thromboplastin time (aPTT), prothrombin time (PT)
Urinalysis	Protein, glucose ketones, bilirubin, urobilinogen, hemoglobin, pH, specific gravity, appearance, color, leukocyte esterase, nitrite Microscopic tests (bacteria, erythrocytes, leucocytes, crystals, casts, epithelial cells, yeast, oval fat bodies, fat, mucous, sperm, trichomonas)
Other laboratory assessments	Human chorionic gonadotropin (hCG) pregnancy test (as needed for women of childbearing potential)

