6.7.4 Clinical Laboratory Assessments

Clinical laboratory assessments including hematology, chemistry, coagulation, and urinalysis will be summarized by cohort and overall for each protocol specified timepoint.

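### Safety laboratories are run locally, but no range-based, shift or CTCAE-graded laboratory table is planned, so Grade 3 or higher values reach summary tables only through investigator AE reporting

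*Protocol*

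**What the plan says.** **Where the tests are run.** Protocol 10.2 states that the safety tests in Table 8 "will be performed by the local laboratory". The synopsis states that "The study will be conducted at 4-5 Phase 1 ophthalmology experienced sites".

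**How they are summarised.** Protocol 9.3.2: "Laboratory evaluations, vital signs assessments, and ECG parameters will be summarized at protocol-specified collection time point". The next sentence adds: "A summary of change-from-baseline at each protocol-specified time point will also be presented". SAP 6.7 repeats both. SAP 6.7.4 says that hematology, chemistry, coagulation and urinalysis results "will be summarized by cohort and overall for each protocol specified timepoint". None of these sections mentions reference ranges, low/normal/high shifts or toxicity grades. SAP 6.7.1, by contrast, sets threshold categories for heart rate, QRS, PR and QTcF.

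**What the stopping rule counts.** One limb in Protocol 7.1 is two or more subjects in a cohort with a CTCAE "Grade 3 or higher clinical or laboratory abnormality that is considered to be related to study drug by the investigator".

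**What happens to abnormal values.** Under Protocol 8.2.4 the investigator records clinically relevant laboratory changes as AEs. Abnormalities associated with the underlying disease do not count as clinically significant unless they are judged more severe than expected. Values considered clinically significant "should be repeated until the values return to normal or baseline".

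**The concern.** Safety is the primary objective of this first-in-human escalation study, and laboratory results are a named basis for escalation in Protocol 4.1. Analysis is descriptive only (SAP 6), so the tables and listings are the whole safety analysis.

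Three things are missing from the laboratory tables.

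- **Grade.** The stopping rule is framed in CTCAE grades, but no output grades a laboratory value. A grade arises only after the value has become an AE, and that step is an open-label clinical judgement which no planned table checks.
- **Reference range.** Values from different laboratories are pooled in raw form, so their extremes have no common scale.
- **Repeats.** The worst value may be on a repeat sample, and the summaries are restricted to scheduled times.

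What is at stake is whether a reader of the safety tables, or the SMC, can see every Grade 3 or higher value by dose without relying on the judgement of clinical significance.

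**Working it through.** The plan gives no figure to reproduce. The check follows a laboratory value through the planned outputs and then sizes the consequences under stated assumptions.

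**1. Route of a Grade 3 or higher value.**

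| Output | Source | Does an abnormal value enter? |
|---|---|---|
| Values and change from baseline | Protocol 9.3.2; SAP 6.7, 6.7.4 | Yes if at a scheduled time, but ungraded and not set against a range |
| TEAE tables of maximum severity and highest relationship | SAP 6.7; grading in Protocol 8.4.3.1 | Only if recorded as an AE |
| TEAE line listing with severity, causality and dose level | SAP 6.7 | Only if recorded as an AE |
| SMC Safety Data Review Summary | Protocol 10.1.5 | As a clinically significant event or an AE |
| Interim listing | SAP 7 | Only clinically significant results |
| eCRF listings | Protocol 9.3.6; SAP 6 | Yes if entered, ungraded |

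Relatedness is assessed on AEs (Protocol 8.4.3.2). A value not recorded as an AE therefore has no relatedness assessment and cannot count toward the limb in 7.1.

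**2. Repeats.** The Schedule of Activities gives laboratory samples at screening, Day 1 predose, before discharge on Day 1, and Day 8: two before dosing and two after. SAP 3.3 summarises by nominal time point, with analysis windows for screening, Day 1 and Days 8-14. A repeat on Days 2-7 has no window. A repeat on Days 8-14 falls inside the follow-up window, but no rule says which value is used.

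**3. Raw values without a range.** Assumed upper limits of normal (ULN) at two laboratories: 35 and 55 U/L. A pooled maximum of 220 U/L is 220/35 = 6.3 x ULN at one and 220/55 = 4.0 x ULN at the other. Where a grade boundary is a multiple of ULN lying between those figures, the same raw maximum falls in different grades.

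Means do not show a single event. With one subject at 6 x ULN and the rest at 0.6 x ULN (assumed), the cohort mean is (11 x 0.6 + 6)/12 = 1.05 x ULN at n = 12 and (2 x 0.6 + 6)/3 = 2.4 x ULN at n = 3.

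**4. Laboratory offsets.** Assumptions: true ALT 25 U/L; laboratory B reads a proportion r higher than laboratory A; B supplies 9/12 subjects in one cohort and 3/12 in another.

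- Difference in raw cohort means with no drug effect: 25 x r x (9/12 - 3/12).
- Difference in mean change with no drug effect, same laboratory for both samples: 0.
- Difference in mean change with a true rise of 10 U/L, same laboratory: 10 x r x 0.5.
- Apparent change in one unaffected subject with baseline at A and post-dose sample at B: 25 x r.

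| r | Raw means (U/L) | Change, no effect | Change, true rise 10 | One subject, mixed laboratories |
|---|---|---|---|---|
| 5% | 0.625 | 0 | 0.25 | 1.25 |
| 10% | 1.25 | 0 | 0.5 | 2.5 |
| 20% | 2.5 | 0 | 1.0 | 5.0 |

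Change from baseline works if one laboratory runs both samples. That is not assured: the SAP does not define laboratory baseline, two pre-dose samples exist, and the general rules in Protocol 8 let routine-care results obtained before consent serve as screening or baseline values.

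**5. How few subjects the limb turns on.** P(at least 2 of n) = 1 - (1-p)^n - n p (1-p)^(n-1), where p is the assumed true rate of related Grade 3 or higher events. At p = 10%, n = 12: 1 - 0.282 - 0.377 = 34.1%; at n = 3, 2.8%. At n = 12 it is 11.8% for p = 5% and 72.5% for p = 20%. The limb depends on individual subjects, so what matters is that each graded value is visible; cohort means do not serve it.

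**The case against.** A reader might infer that the Grade 3 laboratory limb is never tabulated. The documents do not support that. A laboratory change judged clinically relevant becomes an AE, is graded by CTCAE v5.0, enters the maximum-severity table and is listed with causality and dose. The limb also requires relatedness, which the AE route captures and a programmed grade cannot. What remains is narrower: values not recorded as AEs are neither graded nor counted, and the AE tables name severity and relationship without specifying their cross-tabulation.

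A reader might also infer that differences between doses will be laboratory artefacts. Change from baseline is planned, and with no drug effect its expected value is zero under additive or proportional offsets if one laboratory runs both samples. Day 1 predose and pre-discharge samples make that comparison available. The offset problem is therefore confined to raw summaries and to baselines from another laboratory.

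Third, a reader might infer that the SMC would miss an extreme value. Protocol 4.1 has it review all available safety data, including laboratory results; its charter sets the report content and is not among these documents. In cohorts of 3 to 12 a single extreme value would show in subject-level data, and the planned summaries include the maximum. This stands, and it lowers the severity. It does not supply a grade or a reference range, and the outputs the documents do describe for the SMC are filtered by clinical significance.

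Repeats are also not lost: those entered on the eCRF are listed, and Protocol 8.4.4 requires changes in AE severity to be documented. Finally, the number of laboratories is inferred from the 4-5 sites and is not stated.

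**Conclusion.** The gap is real and of minor to moderate weight. Neither document plans a range-normalised, shift or CTCAE-graded laboratory table, although testing is local, the SAP sets such categories for ECG, and the stopping rule refers to laboratory grades. Grade 3 or higher values reach summary tables only through investigator AE reporting, and unscheduled repeats fall outside the laboratory summaries.

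The document facts rest on no assumption. The sizes do: the 6.3 versus 4.0 x ULN contrast, the raw-mean differences of about 0.6 to 2.5 U/L and the mixed-laboratory changes of 1.25 to 5.0 U/L depend on assumed limits, offsets and site mix. They assume at least two laboratories with different calibration or ranges. If all sites shared one laboratory, the pooling concern would fall away, but the missing grades and the handling of repeats would remain. Nothing here shows that the stopping rule cannot operate or that the safety conclusions would be wrong.

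**What to change.** Keep the planned summaries of values and change from baseline, and add the following.

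1. **SAP 6.7.4, baseline.** Define laboratory baseline as the last pre-dose sample, normally Day 1 predose, and flag any subject whose baseline and post-dose samples come from different laboratories.
2. **SAP 6.7.4, shift table.** Tabulate baseline grade against worst post-dose CTCAE v5.0 grade, derived by program from each local laboratory's own range after conversion to common units, and including unscheduled repeats. Present it by dose administered, because cohort 1 is 25 mg in one sub-study and 50 mg in the other.
3. **SMC package.** Provide the listing and count of subjects with Grade 3 or higher values, with the investigator's relatedness assessment beside each, or a note that none was recorded. The stopping rule itself is unchanged.
4. **Protocol 9.3.2.** Add a sentence pointing to the graded table.

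The cost is entry of local reference ranges with the results, one extra programmed table and listing, and SAP text. No additional samples, visits or subjects are needed.

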9.3.3 Analysis of the Secondary Endpoint (Activity)

The number, diameter, and area of post-injection hyper-fluorescent puncta detected on fundus fluorescence images upon injection of AMDX-2011P that were not present prior to injection will be summed and descriptive statistics will be presented for each study eye per cohort.

A positive diagnosis is defined as detection of hyper-fluorescent puncta on fundus fluorescence imaging that were not present prior to injection of AMDX-2011P.

A false negative is defined as an eye from a subject with definite diagnosis and no new hyper-fluorescent puncta detected post-injection of AMDX-2011P via fundus fluorescence imaging that were not present prior to injection.

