All retinal images will be deidentified and sent in batched to a reading center for masked assessment. Assessors will be masked to type of subjects, their disease, dose, clinical status of subjects, and sequence of post-injection images. This provides an objective assessment of the ability of AMDX-2011P to identify amyloidogenic deposits. During the interim analysis (see Section 9.3.8), the SMC may also review representative images to confirm the optimum detection and the residence time and make potential recommendations to the retinal imaging timepoint(s) and/or potential safety assessment modifications.

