6.3 MEASURES TO MINIMIZE BIAS: RANDOMIZATION AND BLINDING

This study is open-label, assessor masked. All retinal images will be sent in batches to a central reading center for masked assessment. Assessors will be masked to type of subjects, their disease status, dose, and sequence of post-injection images. Investigators will not be masked to study drug. Please see Section 8.1.4 for further details on the central reading center procedures.

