8.1.2 Triplicate Fundus Fluorescence (FF) Imaging

FF imaging enables visualization of fluorescent signals in the retina. Conventional and routinely used FF retinal cameras have the appropriate technical specifications to detect the hyper-fluorescent signal generated by AMDX-2011P-bound amyloidogenic proteins.

Predose images will be captured using fundus autofluorescence (FAF) imaging. Immediately after IV injection with study drug, FAF images and/or videos will be continuously captured until 2 minutes post-injection to assess the influx of the dye into the retina. After that, the remainder of the static images will be captured using FAF imaging. FF images (excluding conventional fundus photos) at all time points will be captured with the Heidelberg Spectralis 55-degree lens and the FAF settings of the device, using the central fixation target. Additional FF images may also be captured using the Optos UWF imaging modality or offset (no central fixation target) 55-degree Heidelberg FAF modality at select time points. Complete instructions information will be provided in the imaging section of the Study Reference Manual. Images will be quality checked and exported per the respective retinal imaging device User Manual. All FF images will be prepared and transferred to a central reading center for review. Each FF image will be reviewed by the masked reading center assessors using the respective retinal imaging device's native review software. The images will be assessed for image quality based on the respective devices image quality criteria.

On Day 1, retinal imaging will be performed with both Spectralis and Optos devices in triplicate as shown in Table 5. Due to intensity of imaging, images taken outside the windows will not be considered protocol deviation.

Table 5 Collection Timepoints for Fundus Fluorescence (FF) Imaging

Day 1 Time point	Window	Spectralis	Optos
Predose		X	X
0-1 min		Video	
2 min		X	
5 min		X	
10 min	±2	X	X
30 min	±5	X	X
1hr	±10	X	X
2hr	±10	X	X
4hr	±10	X	X
8hr	±10	X	X

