8.1.3 Optical Coherence Tomography (OCT) and OCT Angiography (OCT-A) Imaging

OCT is a non-contact imaging technique which generates high resolution cross-sectional images of the retina and its corresponding layers. OCT images will be acquired as specified in the SoA (Section 1.3). The Heidelberg Spectralis device will be used to capture volumetric structural

OCT and OCT-A images. The combination of FF and OCT/OCT-A images will enable for detection and mapping of amyloidogenic protein distribution across the fundus and across different retinal layers and retinal plexuses. For each imaging modality, OCT and OCT-A, the images will be assessed for image quality based on the respective device's image quality criteria.

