8.1.4 Central Retinal Image Center (CRIC)

All acquired images will be checked for quality, and subjects' identifiers will be removed by study personnel at investigational site. Deidentified images will be sent to a central imaging center specialized in assessing retinal images for detection and quantification of hyper-fluorescent puncta. Each assessor at the CRIC will be masked to the subject's disease status and sequence of post-injection images. Images will be batched and read at time of the interim analysis and final analysis, or more frequently at the request of SMC. Upon receiving deidentified images from the clinical site, quality assurance (QA) officer at the CRIC will review all images to confirm that the images sent meet the quality, quantity, and image acquisition criteria defined in the protocol. The QA officer will confirm that the images are labeled appropriately and that they were obtained by a certified imager. Once the QA officer reviews and confirms the integrity of each image batch, the images will be randomized and submitted to the masked assessors for grading. At the time of the interim and final analyses, the randomized masked images submitted to the assessors will be evaluated for image quality and for the number of distinct hyper-fluorescent puncta. Additional information will be provided in the imaging section of the Study Reference Manual.

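### Any new puncta make an eye positive, on 24 post-dose against 3 pre-dose stills: a spot missed before dosing can only raise apparent sensitivity, by an amount the study cannot see

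*Protocol*

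**What the plan says.** **The call.** Protocol 9.3.3: "A positive diagnosis is defined as detection of hyper-fluorescent puncta on fundus fluorescence imaging that were not present prior to injection of AMDX-2011P". An eye is a false negative only if it shows no new puncta at all. SAP 6.8 repeats both definitions and names the first a true positive. Neither gives a minimum count or says how replicate images combine into the call.

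**The images.** Protocol 8.1.2: "On Day 1, retinal imaging will be performed with both Spectralis and Optos devices in triplicate as shown in Table 5". Table 5 lists one pre-dose and eight post-dose time points for Spectralis stills. The Schedule of Activities also marks fundus fluorescence imaging at Day 8. The Imaging Population (Protocol 9.2) requires "at least one set of acceptable color fundus photographs and OCT scans predose and at least 3 acceptable quality fundus autofluorescence images" in each of two sessions, pre-dose and 5 minutes to 1 hour post-dose.

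**The reading.** Protocol 4.1: "Assessors will be masked to type of subjects, their disease, dose, clinical status of subjects, and sequence of post-injection images". Protocol 6.3: "Assessors will be masked to type of subjects, their disease status, dose, and sequence of post-injection images". Protocol 8.1.4 names only "disease status and sequence of post-injection images", and adds that after quality checks "the images will be randomized and submitted to the masked assessors for grading". The Synopsis also describes masked assessment in random order, and 8.1.2 has each fluorescence image reviewed by masked assessors. Further detail is left to the Study Reference Manual, which is not among the documents.

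**Other modalities.** Protocol 8.1.3: "The combination of FF and OCT/OCT-A images will enable for detection and mapping of amyloidogenic protein distribution". The positive and false-negative definitions, however, are worded on fundus fluorescence imaging alone.

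**The concern.** New means seen after injection and not before, so the call depends on how hard one looks on each side. Here there are eight times as many Spectralis stills after dosing as before. Some retinal spots may be faint, unrelated to the tracer and visible in only some images. Such a spot has 3 chances to be recorded as baseline and up to 24 chances to be called new.

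The error has one direction. It can turn an eye that would have been a false negative into a positive. It cannot do the reverse, so apparent sensitivity can only go up.

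Two features make it hard to see in the results:

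- Every subject has a confirmed diagnosis (Protocol 9.1), so no unaffected group shows how often such spots are called new.
- The Imaging Population admits eyes with very different numbers of post-dose images, so the chance of a positive call can differ between eyes for reasons unrelated to disease or dose.

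Because new is a pre/post comparison, knowing which image is pre-dose is the information most able to influence the reader. The masking statements do not mention it.

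**Working it through.** **1. The plan's own figure.** Protocol 9.1 assumes about 10% false negatives and a prevalence of 0.5 per disease, and states sensitivity of about 0.8. Reading the 10% as a share of all subjects reproduces it: (0.5 − 0.1)/0.5 = 0.80. With the SAP 3.1 pooled prevalence, (0.75 − 0.1)/0.75 = 0.867, consistent with its claim of at least 0.8. The stated specificity cannot be derived: no false-positive rate is given and no unaffected subject is enrolled. The planned 10% refers to subjects while the rule is per eye, so the link is loose. Still, false negatives are the quantity on which the planned sensitivity rests.

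**2. Image counts (Table 5, in triplicate).**

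- Spectralis stills, post-dose: 2, 5, 10 and 30 min, 1, 2, 4 and 8 hr = 8 time points; 8 × 3 = 24.
- Spectralis stills, pre-dose: 1 × 3 = 3.
- Optos: 6 × 3 = 18 post-dose against 3 pre-dose. Both devices together: 42 against 6.
- Minimum for the Imaging Population, if 5 minutes to 1 hour is one session: 3 pre-dose and 3 post-dose. Eyes in one analysis may then have from 3 to 24 post-dose Spectralis stills.

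**3. Illustration.** Assume one faint non-tracer spot per eye, seen in any one image with chance d, and images read separately with no look-back to the pre-dose image. The documents give neither d nor the correlation between images, so both are varied. The spot is called new if missed in all pre-dose images and seen in at least one post-dose image.

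- Images independent: (1 − d)³ × [1 − (1 − d)^k], with k = 24 or 3. At d = 0.10: 0.729 × 0.920 = 67%, against 0.729 × 0.271 = 20%.
- Triplicates fully correlated, time points independent: (1 − d) × [1 − (1 − d)^t], with t = 8 or 1. At d = 0.10: 0.9 × 0.570 = 51%, against 0.9 × 0.1 = 9%.
- Correlation ρ shared by all images (beta-binomial): a = d(1 − ρ)/ρ, b = (1 − d)(1 − ρ)/ρ, P0(n) = B(a, b + n)/B(a, b). Called new = P0(3) − P0(27), against P0(3) − P0(6).

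Chance (%) that the spot is called new, 24 post-dose stills / 3 post-dose stills, each against 3 pre-dose:

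| Visibility d | Independent | Triplicates fully correlated | ρ = 0.5 | ρ = 0.9 | ρ = 1 |
|---|---|---|---|---|---|
| 1% | 21 / 3 | 8 / 1 | 2.0 / 0.6 | 0.3 / 0.1 | 0 / 0 |
| 5% | 61 / 12 | 32 / 5 | 8.9 / 2.8 | 1.2 / 0.4 | 0 / 0 |
| 10% | 67 / 20 | 51 / 9 | 15.5 / 5.0 | 2.3 / 0.7 | 0 / 0 |
| 20% | 51 / 25 | 67 / 16 | 22.9 / 8.0 | 3.9 / 1.3 | 0 / 0 |
| 50% | 12.5 / 11 | 50 / 25 | 20.4 / 8.7 | 5.6 / 1.9 | 0 / 0 |
| 90% | 0.1 / 0.1 | 10 / 9 | 3.3 / 1.8 | 1.8 / 0.6 | 0 / 0 |

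The second figure in each cell also shows what a comparison of one post-dose triplicate with the pre-dose triplicate would give. It is lower in most settings, but not zero.

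**The case against.** Several points on the other side stand.

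- **The reading is better controlled than the rule alone suggests.** The Synopsis, 8.1.2 and 8.1.4 describe randomised, masked review of each image, and SAP 6.8 counts distinct new spots, which points to unique spots rather than repeated sightings. A reader might infer that assessors are unmasked to pre/post status. The documents do not support that. They neither say readers know which images are pre-dose nor say they do not, and the manuals may settle it.
- **Images of the same eye are likely to agree.** Same device, same field and same fixation make strong correlation plausible, and at ρ = 0.9 no figure above exceeds 5.6%. Exclusion criterion 5 also removes eyes whose autofluorescence would significantly hinder telling new signal from old. Pre-dose colour photographs and OCT add baseline evidence, though the rule does not say how they enter.
- **Many post-dose time points are needed.** With residence time unknown, the any-spot result is a reasonable summary and should stay.
- **Some of the needed data are already planned.** The exploratory analyses in SAP 6.10 require counts over time, and the interim listings in SAP 7 show pre- and post-dose counts (none for MSA).
- **No single reading method is clearly best.** Unlabelled separate reading removes expectation bias but also removes look-back to the pre-dose image, which is how a missed baseline spot might be caught.

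None of this changes the unequal number of looks before and after dosing, or the fact that the call turns on a single new spot.

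**Conclusion.** The point holds as a matter of direction. Followed as written, the any-spot rule gives a non-tracer spot more chances to be seen after dosing than before. This error can only raise apparent sensitivity, and the study has no unaffected subjects in whom to measure it.

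Its size is unknown. Over the assumed range the chance that such a spot is called new runs from 0 to 67%. It is zero if a spot is seen either in every image or in none. It is small when pre- and post-dose images agree strongly. It is large only for spots seen in a minority of images (up to about half, if replicates agree fully) whose visibility varies from image to image. The 24-to-3 count assumes that the triplicate is per eye.

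A reader might take the larger figures as an estimate of inflation, or conclude that positives in this study are artefacts. Neither follows: visibility, correlation and the presence of such a spot are all assumed. Nor is any formal test affected. Safety is primary, and SAP 6 plans no inference. What is affected is how the secondary activity result, and the label true positive, are read.

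**What to change.** (a) Keep the any-spot result. Beside it, report positivity per time point, comparing one post-dose triplicate with the pre-dose triplicate from the same device. Report the number of acceptable pre- and post-dose images per eye, and state whether Day 8 images count towards a positive call.

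(b) State in the SAP, or by reference to the imaging manual, whether readers know pre/post status when they mark puncta, and how new is derived across replicates. The choice between unlabelled separate reading and side-by-side reading can stay with the sponsor, provided it is stated.

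**Cost.** Modest extra tabulation from images already planned, plus a few sentences of SAP or manual text. No new images, subjects or visits are needed. Item (a) reduces the excess but does not remove it, and neither item supplies the missing unaffected group, whose absence follows from a safety restriction on healthy volunteers.
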